5.3.1.1.2. Suppressed HBV DNA

HBV DNA < LLOQ and HBV DNA TND will be evaluated over time.

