In a recent systematic review that included 25 studies mainly from Asia, identification of predictors of virologic relapse and HBsAg loss after stopping NA led to conflicting results, partly due to the heterogeneity of the studies and low rate of HBsAg loss (2%).²⁹ Lower baseline HBsAg level was the only statistical baseline factor for off-therapy HBsAg seroclearance in a large cohort of 1075 HBeAg-negative patients in Taiwan.¹⁸ Studies conducted in Asia have reported a lower estimated annual incidence of 1.78% of HBsAg loss highlighting potential differences among Asians and Caucasians.¹⁸ A recent European retrospective, observational cohort study that included 198 NA-treated CHB patients who stopped NA treatment after HBeAg seroconversion showed 7-fold higher annual HBsAg seroclearance rates in Caucasian patients compared to non-Caucasians.³⁴

After stopping NA treatment, it is expected that most of the patients will have rebound of HBV DNA. This was reported in the Hadziyannis study where all patients had an initial rebound of HBV DNA and 76% showed an alanine aminotransferase (ALT) flare suggesting that virologic relapse might be an important trigger for immune response that could lead to subsequent HBsAg loss. This was also reported in a recent prospective study showing that level of HBV DNA after stopping NA was the most important factor for subsequent HBsAg decline.¹³ Therefore factors that may influence virologic relapse should be taken into consideration. Some recent studies have reported that patients treated with TDF experience virologic relapse significantly earlier than those receiving ETV. In a randomized study of 220 HBeAg-negative Asian patients who stopped treatment, 71% (47 of 66) treated with TDF had virologic relapse by Week 12, whereas 4.5% of patients (7 of 154) treated with ETV had virologic relapse in the same period ($p < 0.0001$), while the overall virologic relapse rate was similar.¹² Similarly, in a retrospective study that included 234 HBeAg-negative Asian patients who stopped treatment, median time to virologic relapse was 18 weeks (TDF) versus 33 weeks (ETV).²⁰

Given the reported influence of race (Asian versus non-Asian), type of NAs (TDF/tenofovir alafenamide [TAF] versus ETV) and baseline HBsAg level on virologic relapse and subsequently HBsAg seroclearance, those 3 elements will be included as stratification factors in the current study.

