9.4.1.2. Secondary and Exploratory Efficacy Endpoints

Descriptive statistics will be used for all efficacy endpoints which will be summarized by intervention arm and study phase. Comparisons between intervention arms will be done with no adjustment for multiplicity. Specific key selected endpoints may be analyzed using suitable categorical data approaches (eg, Cochran-Mantel-Haenszel or logistic regression for proportions or other categorical type of endpoint), longitudinal repeated measures models (eg, for continuous types of variables), or survival analysis based on the Kaplan-Meier estimates (for time-to-event variables), as appropriate. Details will be described in the SAP.

To evaluate the efficacy at the end of treatment, the proportion of participants with HBsAg seroclearance and the proportion of participants with HBV DNA <LLOQ at Week 48, respectively, will be tabulated by study intervention arm. Between arm comparisons for both endpoints will be evaluated using the stratum-adjusted Mantel-Haenszel difference in

proportions, where the stratification factors screening HBsAg level (<1,000 IU/mL or \geq 1,000 IU/mL), race (Asian versus non-Asian) and type of NA (TDF/TAF versus ETV) determine the strata and corresponding 90% cIs.

The efficacy of the study intervention during the follow-up phase will also be evaluated. The proportion of participants with HBsAg seroclearance at Week 96 without restarting NA treatment, the proportion of participants with HBV DNA <LLOQ at Weeks 72 and 96, respectively, the proportion of participants achieving partial response (HBV suppression without restarting NA treatment) at different time points during follow-up, the proportion of participants with flares (virologic, biochemical, and clinical), and the proportion of participants requiring NA re-treatment during follow-up will be tabulated by intervention arm. The comparison between the intervention arms will be done using the stratum-adjusted Mantel-Haenszel difference in proportions, as described above. A similar analysis will be conducted for the proportion of participants with HBsAg seroclearance 24 and 48 weeks, respectively, after stopping all study interventions without restarting NA treatment.

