5.3. Major Secondary Endpoints

See Section 1.1 for a list of the secondary endpoints. All major secondary endpoints will be analyzed using observed case data. Additional analyses with specific imputation methods for missing data are added for selected endpoints.

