5.3.1.1.9. ALT Normalization

ALT elevation at baseline is defined as $ALT \geq ULN$. A participant with ALT elevation at baseline achieves ALT normalization if his/her ALT value post-baseline is $< ULN$ at any given time point.

Participants who achieve ALT normalization on treatment and off treatment but without restarting NA treatment will be evaluated over time.

Participants who were re-treated with NA and who have $ALT \geq ULN$ before NA re-treatment and reach ALT normalization after NA re-treatment during follow-up will be evaluated.

Additionally, for those participants who restarted NA treatment during the follow-up, the participants who reach $ALT < ULN$ and who have ALT less than their nadir value during the study will be evaluated.

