5.3.1.4. Endpoints for Correlation

Correlations between baseline characteristics, and on-treatment HBV blood markers and/or their change from baseline at Week 24 and 48 with off-treatment endpoints will be evaluated. The list of HBV blood markers, including but not limited to, are defined below:

Off treatment HBV marker	Baseline Characteristics/On treatment HBV marker
HBsAg change from baseline at FU Week 12	
 • Age • Baseline NA treatment duration • HBsAg value at baseline • HBsAg change from baseline at Week 24 • HBsAg change from baseline at Week 48
HBsAg change from baseline at FU Week 24	
 • Age • Baseline NA treatment duration • HBsAg value at baseline • HBsAg change from baseline at Week 24 • HBsAg change from baseline at Week 48
HBsAg change from baseline at FU Week 48	
 • Age

Off treatment HBV marker	Baseline Characteristics/On treatment HBV marker
	
 • Baseline NA treatment duration • HBsAg value at baseline • HBsAg change from baseline at Week 24 • HBsAg change from baseline at Week 48
HBsAg seroclearance at FU week 24 (Yes;No)	
 • Age • Baseline NA treatment duration • HBsAg value at baseline • HBsAg change from baseline at Week 48 • HBsAg value at Week 48 • HBsAg seroclearance at week 24 (Yes;No) • HBsAg seroclearance at week 48 (Yes;No) • Anti-HBe antibodies status at week 48 (Positive:Negative)
HBsAg seroclearance at FU week 48 (Yes;No)	
 • Age • Baseline NA treatment duration • HBsAg value at baseline • HBsAg change from baseline at Week 48 • HBsAg value at Week 48 • HBsAg seroclearance at week 24 (Yes;No) • HBsAg seroclearance at week 48 (Yes;No) • Anti-HBe antibodies status at week 48 (Positive:Negative)
Partial cure (Yes;No) at FU Week 24 (Yes;No)	
 • Age • Baseline NA treatment duration • HBsAg value at baseline • HBsAg value at Week 48 • HBsAg seroclearance at week 24 (Yes;No) • HBsAg seroclearance at week 48 (Yes;No) • Anti-HBe antibodies status at week 48 (Positive:Negative)
Partial cure (Yes;No) at FU Week 48 (Yes;No)	
 • Age • Baseline NA treatment duration • HBsAg value at baseline • HBsAg value at Week 48 • HBsAg seroclearance at week 24 (Yes;No) • HBsAg seroclearance at week 48 (Yes;No) • Anti-HBe antibodies status at week 48 (Positive:Negative)

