5.3.2.1.1. Suppressed HBV DNA

The number of occurrences each subject has HBV DNA <LLOQ will be determined and summarized by intervention arm using frequency distributions and descriptive statistics. Additionally, the number of occurrences will be displayed graphically.

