5.3.2.2.1. HBsAg and HBV DNA

The change from baseline value to the nadirs (i.e. maximum decrease for each participant) in HBsAg and HBV DNA will be summarized descriptively by intervention arm. Box plots of the changes to nadirs in HBsAg and HBV DNA will display the distribution by intervention arm.

Change from baseline based on \log_{10} transform for quantitative HBsAg and HBV DNA will be analyzed using mixed effects model for repeated measures [MMRM]) including intervention arm, analysis time point (week), their interaction, and 3 randomization stratification factors (screening HBsAg level [$<1,000$ IU/mL or $\geq 1,000$ IU/mL], race [Asian versus non-Asian] and type of NA [TDF/TAF versus ETV]) and baseline blood marker categorical variable as fixed effects. In addition, the above model will be augmented with an intervention arm-by-analysis week interaction term (i.e. treatment-by-time interaction term) to evaluate the change of treatment effect over time and the intervention arm-by-baseline interaction term. The covariance structure will include a random intercept at the level of the participant to capture between-participant variability, while within-participant variability will be captured with an unstructured (type=UN) covariance matrix. In case of convergence problems, simpler variance-covariance structures such as Toeplitz or AR (1) will be considered. The selection of any of these structures will be determined after exploration of the observed correlation structure. The LS mean of change from baseline, standard error (SE), 90% confidence interval (CI) and p-values will be provided.

Descriptive statistics on actual values (original unit and \log_{10} transformed values) and changes from baseline (\log_{10} transformed values) at end of treatment in HBsAg and HBV DNA will be summarized by study intervention arm by outcome response (i.e. by functional cure status at Week 72, and by partial cure status at Week 72).

Spaghetti plots for both absolute values and changes from baseline of HBsAg and HBV DNA will be presented over time per blood marker by intervention arm and by selected subgroups (e.g. HBV Genotype) and by outcome response (i.e. by functional cure status at Week 72, and by partial cure status at Week 72).

Cross-tabulations overtime and overall of quantitative versus qualitative HBsAg values will also be presented.

Shift tables in HBV DNA categories from baseline will also be summarized by study intervention arm.

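### Follow-up HBV DNA analyses have no NA-restart rule, so rescued relapsers count as suppressed and the arm comparison is biased if restart rates differ

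*SAP*

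**What the plan says.** For HBV DNA suppression, SAP 5.3.1.1.2 says only that "HBV DNA < LLOQ and HBV DNA TND will be evaluated over time". SAP 5.3.2.1.1 adds that "The number of occurrences each subject has HBV DNA <LLOQ will be determined and summarized by intervention arm". The HBV DNA level cut-offs in SAP 5.3.1.1.5, and the values and changes over time in SAP 5.3.1.2 and 5.3.2.2, are equally unconditional. For the model, SAP 5.3.2.2.1 says that "quantitative HBsAg and HBV DNA will be analyzed using mixed effects model for repeated measures [MMRM]) including intervention arm, analysis time point (week" and further terms; it neither limits the time points to the treatment phase nor drops values after NA restart. The general rule in SAP 5.3 is that "All major secondary endpoints will be analyzed using observed case data".

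Protocol 9.4.1.2 plans a stratum-adjusted Mantel-Haenszel comparison of "the proportion of participants with HBV DNA <LLOQ at Weeks 72 and 96, respectively", again without a restart condition. The endpoints on either side of it in the same sentence (HBsAg seroclearance at Week 96 and partial response) do carry one.

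Elsewhere the plan handles restart explicitly. The primary estimand counts it as non-response (SAP 5.2.2). The emphasised off-treatment HBsAg seroclearance endpoints (5.3.1.1.1), the joint HBsAg/HBV DNA thresholds (5.3.1.1.3) and partial cure (5.4.1.1.1) require no re-treatment, and treatment failure (5.4.1.1.5) includes it as a reason. For ALT, "Participants who achieve ALT normalization on treatment and off treatment but without restarting NA treatment will be evaluated over time".

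**The concern.** Follow-up is meant to show what the regimen achieves once all treatment has stopped. The protocol's own rationale is that "After stopping NA treatment, it is expected that most of the patients will have rebound of HBV DNA". Under Protocol 6.7, NA is restarted for an HBV DNA value above 100,000 IU/mL, a confirmed value above 20,000 IU/mL, or a confirmed value above 2,000 IU/mL with ALT above 5 times ULN, among other criteria. Protocol 2.3.1.2 says that NA brings HBV DNA close to or below the LLOQ. Protocol 1.3.2 keeps restarted participants, and those who could not stop NA, in follow-up with visits at least every 12 weeks when stable.

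Rescue is therefore triggered by the variable being analysed, and it then moves that variable in the favourable direction. As written, a participant who relapsed, restarted NA and was re-suppressed is recorded as HBV DNA <LLOQ and adds a low value to the MMRM. If one arm needs more rescue, it gains more of these values.

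**Working it through.** **The plan's own figure.** The documents give no restart or re-suppression rates. The one design figure is power above 91% for the primary endpoint (80 versus 40 participants, 25% versus 5%, one-sided 0.05). It reproduces: 91.7% by exact enumeration of the unstratified Mantel-Haenszel test, 90.2% by the pooled normal formula. This point does not alter it, because restart between Weeks 48 and 72 is already non-response.

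**Inputs.** From the documents: the observed-case rule (SAP 5.3), the restart criteria (Protocol 6.7), the effect of NA on HBV DNA (Protocol 2.3.1.2), and the value of 15 IU/mL imputed for detected results below LLOQ (SAP Table 3). All rates and off-NA levels below are assumptions.

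**Proportion <LLOQ.** Let a be the share of the arm that is off NA and <LLOQ, r the share restarted, and q the share of restarted participants who are <LLOQ at the visit. Counting restart as failure gives a; the analysis as written gives a + r × q.

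| | Active | Control | Difference |
|---|---|---|---|
| a (assumed) | 25% | 15% | +10 points |
| r (assumed) | 10% | 30% | |
| a + r × 0.80 | 0.25 + 0.08 = 33% | 0.15 + 0.24 = 39% | −6 points |

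**When the sign changes.** The difference as written is (a1 − a2) + q × (r1 − r2). With a true +10 points and q = 80%, it turns negative once the restart gap exceeds 0.10 / 0.80 = 12.5 points.

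**Range.** Let s be the share <LLOQ among those not restarted, set equal in both arms. As written, the rate is (1 − r)s + rq; with restart as failure it is (1 − r)s. Take s = 20%, q = 80%, and restart 10% versus 30%:
- as written: 0.18 + 0.08 = 26% versus 0.14 + 0.24 = 38%, a difference of −12 points;
- restart as failure: 18% versus 14%, a difference of +4 points.

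Over s of 20% to 40%, q of 60% to 95%, active restart of 10% and control restart of 20% to 50%, the difference as written runs from −2 to −30 points. With restart as failure it runs from +2 to +16 points. With restart at 20% in both arms, both differences are zero.

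**Mean log10 HBV DNA.** Assume 2.5 log10 if not restarted. For restarted participants assume 4.3 log10 (20,000 IU/mL) had they stayed off NA, and log10(15) = 1.18 on NA. Restart is 10% versus 30%.
- Off NA: 0.9 × 2.5 + 0.1 × 4.3 = 2.68 versus 0.7 × 2.5 + 0.3 × 4.3 = 3.04. The difference is −0.36, in favour of active.
- As written: 0.9 × 2.5 + 0.1 × 1.18 = 2.37 versus 0.7 × 2.5 + 0.3 × 1.18 = 2.10. The difference is +0.26 before rounding the means, against active.

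**Correlation outcomes.** SAP 5.3.1.4 lists nine. Partial cure and treatment failure, each at FU Weeks 24 and 48, carry the restart condition through their definitions. The other five do not state one: HBsAg change at FU Weeks 12, 24 and 48, and HBsAg seroclearance at FU Weeks 24 and 48 (for example "HBsAg seroclearance at FU week 48 (Yes;No").

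**The case against.** Much of the off-NA picture is already planned. SAP 5.3.1.1.3 tabulates HBV DNA <LLOQ, with and without HBsAg loss, at 12, 24, 36 and 48 weeks after stopping everything without re-treatment. Adding the two rows gives off-NA suppression. Partial cure is compared between arms, as is the proportion needing re-treatment, so an imbalance in restart would be visible. The stated objective also covers markers during intervention and follow-up, so an all-values summary is a legitimate treatment-policy description. The affected analyses are secondary and unadjusted for multiplicity, and SAP 5.3.2.1 does not list HBV DNA <LLOQ among the binary endpoints to be compared.

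All of this stands, and it limits the weight of the point. It does not close the gap. SAP 5.3.1.1.3 leaves open whether a restarted participant is a failure or leaves the denominator, and its result would sit beside a different <LLOQ rate from 5.3.1.1.2. The protocol still plans a formal Week 72 and 96 comparison, and the MMRM yields p-values.

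A reader might infer that the HBsAg analyses also flatter the rescued arm. The documents do not support that: Protocol 2.1 puts HBsAg seroclearance on NA at around 3% and describes HBsAg loss after NA is stopped. A reader might also infer that none of the correlation outcomes accounts for restart, but four of the nine do. For the remaining five, the column heading refers to off-treatment markers, and the flare section defines off-treatment as after stopping NA too, but 5.3.1.4 does not apply that definition.

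**Conclusion.** The gap is real for follow-up HBV DNA: suppression over time, counts of suppressed visits, level cut-offs, means, the MMRM, and the Protocol 9.4.1.2 comparison at Weeks 72 and 96. As written, these pool on-NA and off-NA values and count rescued relapsers as suppressed.

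Bias in the arm comparison is conditional. With equal suppression and re-suppression rates it needs unequal restart rates; it then runs towards the arm with more restarts and can change the sign. The sizes shown are illustrations, and it would be wrong to read them as a prediction or the bias as certain.

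For HBsAg the issue is only that on-NA and off-NA values are mixed; no direction is established. The primary endpoint, the emphasised off-treatment HBsAg seroclearance endpoints, the joint thresholds, partial cure and treatment failure already handle restart. The point should be corrected, but it does not threaten the main conclusion of the trial.

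**What to change.** 1. In SAP 5.3.1.1.2, 5.3.1.1.5 (HBV DNA level cut-offs) and 5.3.2.1.1, and for the Week 72 and 96 comparison in Protocol 9.4.1.2, count a participant at a follow-up time point as achieving the endpoint only if NA was stopped and not restarted before it. Participants who restarted or never stopped NA count as not achieved and stay in the denominator. Exempt the planned analyses of response after restart: the post-restart proportions in Protocol 9.4.1.2, the change from NA restart in SAP 5.3.1.1.5, and the decline analysis in SAP 5.4.1.2.1.
2. In SAP 5.3.2.2 and 5.3.2.2.1, for follow-up visits, present the HBV DNA and HBsAg summaries and the MMRM without values on NA, and keep the all-values version as supplementary. State missing-at-random after restart as an assumption: Protocol 6.7 also allows earlier restart at the investigator's discretion, and immediate restart above 100,000 IU/mL leaves few unrestarted participants at high levels to inform the model.
3. In SAP 5.3.1.4, add the no-restart condition to the five HBsAg outcomes only.

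The cost is a SAP wording change and a little programming; SAP 5.3.1.1.8 already identifies actual restarts from the NA administration CRF page. The downside is fewer off-NA values at late follow-up visits.

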5.3.1.1.3. Thresholds Based on HBsAg and HBV DNA

The following blood marker reduction/seroclearance thresholds over time on treatment, and at 12, 24, 36 and 48 weeks, respectively, after stopping all study interventions (including NA) and not having NA re-treated will be evaluated.

- **HBsAg <LLOQ and HBV DNA**
 - HBsAg <LLOQ and HBV DNA <LLOQ**
 - HBsAg <LLOQ and HBV DNA \geq LLOQ
- **HBsAg \geq LLOQ and HBV DNA <2,000 IU/ml**
 - HBsAg \geq LLOQ and HBV DNA <LLOQ**
 - HBsAg \geq LLOQ and LLOQ \leq HBV DNA <2,000 IU/ml (See partial cure in Section 5.4.1.1.1)
- **HBsAg \geq LLOQ and HBV DNA \geq 2,000 IU/ml**
 - HBsAg <100 IU/mL and HBV DNA \geq 2,000 IU/ml
 - HBsAg \geq 100 IU/mL and HBV DNA \geq 2,000 IU/ml

** HBV DNA<LLOQ will be summarized by DNA TD, TND and overall.

Due to the exploratory objectives of this Phase 2b study, additional blood marker reduction/seroclearance thresholds may also be added at a later point in time according to the clinical interest.

5.3.1.1.4. HBsAg Seroconversion

Seroconversion of HBsAg is defined as having achieved HBsAg seroclearance and appearance of anti-HBs antibodies.

The seroconversion will only be assessed at the time points when the anti-HBs antibodies assessment is available. If the HBsAg value is missing at that specific time point, then the non-missing lab test closest to that specific timepoint will be used. If the non-missing lab test before and after the specific timepoint fall equidistant from the target timepoint, the later one will be used to impute the missing value.

Appearance of anti-HBs antibodies is defined as a baseline anti-HBs antibodies (quantitative) <LLOQ and a post-baseline assessment \geq LLOQ. A sensitivity analysis will be conducted using the threshold of 10 mIU/mL, i.e. appearance of anti-HBs antibodies is defined as a baseline anti-HBs antibodies (quantitative) <10 mIU/mL and a post-baseline assessment \geq 10 mIU/mL.

5.3.1.1.5. HBsAg and HBV DNA cut-offs

The cut-offs for HBsAg level are as follows:

- <1000 IU/mL
- <100 IU/mL
- <10 IU/mL
- <1 IU/mL
- <0.05 IU/mL

The cut-offs for HBsAg change from baseline are as follows:

- decrease by $\geq 0.3 \log_{10}$ IU/mL
- decrease by $\geq 0.5 \log_{10}$ IU/mL
- decrease by $\geq 1 \log_{10}$ IU/mL
- decrease by $\geq 2 \log_{10}$ IU/mL
- decrease by $\geq 3 \log_{10}$ IU/mL
- decrease by $\geq 4 \log_{10}$ IU/mL

The cut-offs for HBV DNA are as follows:

- <LLOQ
- <LLOQ TND
- <LLOQ TD
- <60 IU/mL
- <200 IU/mL
- <2000 IU/mL
- <20000 IU/mL
- <100000 IU/mL

HBV DNA change from time of NA re-start

- decrease by $\geq 1 \log_{10}$ IU/mL
- decrease by $\geq 2 \log_{10}$ IU/mL
- decrease by $\geq 3 \log_{10}$ IU/mL
- decrease by $\geq 4 \log_{10}$ IU/mL
- decrease by $\geq 5 \log_{10}$ IU/mL

5.3.1.1.6. Flares

The criteria based on blood markers/lab tests for each of the flare types are defined as below.

a) Virologic flare is defined as follows:

Derivation 1. This derivation of virologic flare will be assessed only for those participants who are off-treatment and had HBV DNA<LLOQ at the last observed point on all study treatments.

The start date of a virologic flare is defined as the first date of two consecutive visits with HBV DNA > 200 IU/mL. The end date of the same virologic flare is defined as the first date when HBV DNA value returns to ≤ 200 IU/mL or the date of treatment restart, whichever comes first. Each virologic flare will be categorized based on the confirmed (i.e., two consecutive values) peak HBV DNA above any of the four thresholds within the start and end date of that flare as follows: 100,000 IU/mL, 20,000 IU/mL, 2,000 IU/mL and 200 IU/mL.

Derivation 2. This derivation of virologic flare will be assessed only for those participants who are off-treatment and had HBV DNA \geq LLOQ at the last observed point on all study treatments.

The start date of a virologic flare is defined as the first date of two consecutive visits with HBV DNA \log_{10} increase from end of treatment $> 1 \log_{10}$. The end date of the same virologic flare is defined as the first date when HBV DNA \log_{10} increase from end of treatment returns to $\leq 1 \log_{10}$ or the date of treatment restart, whichever comes first. Each virologic flare will be categorized based on the confirmed (i.e., two consecutive values) peak HBV DNA above any of the three thresholds within the start and end date of that flare as follows: 1 \log_{10} , 2 \log_{10} and 3 \log_{10} .

- 1 (Yes) = confirmed** HBV DNA > peak threshold.
- 0 (No) = at least one off-treatment HBV DNA measurement available and not meeting the criteria of confirmed HBV DNA > peak threshold.
- 2 (Not applicable) = no off-treatment HBV DNA quantitative measurements available.

b) Biochemical flare is defined as follows:

- 1 (Yes) = confirmed** ALT and/or AST $\geq 3x$ ULN and $\geq 3x$ nadir (ie, lowest value observed up to the start of the flare)
- 0 (No) = otherwise

The start date of a biochemical flare is defined as the first date of two consecutive visits with ALT and/or AST $\geq 3x$ ULN and $\geq 3x$ nadir. The end date of the same biochemical flare is defined as the first date when there is a 50% reduction from the peak ALT and/or AST level & $< 3x$ ULN.

c) Clinical flare is defined as follows:

Clinical flare will be assessed with both derivations specified above for virologic flare.

- 1 (Yes)= confirmed^{**} HBV DNA > peak threshold and confirmed^{**} ALT and/or AST ≥ 3 x ULN and ≥ 3 x nadir (ie, lowest value observed up to the start of the flare).
- 0 (No) = otherwise

A clinical flare occurs when a virologic flare and biochemical flare overlap in time. However, if there is no overlap in time, a clinical flare occurs when a virologic flare ends prior to a biochemical flare starting, and the end date of the virologic flare is within 4 weeks of the biochemical flare start date. The start date of a clinical flare is defined as the minimum start date of the virologic flare and the biochemical flare. The end date of a clinical flare is defined as the maximum end date of the virologic flare and biochemical flare, i.e., the later date of HBV DNA ≤ 200 IU/mL (or ≤ 1 log₁₀) and 50% reduction from the peak ALT and/or AST level.

^{**} Confirmed means that the criterion should be fulfilled at 2 or more consecutive time points or at the last observed time point.

The virologic and clinical flares will be assessed only off-treatment, while biochemical flares will be identified on treatment and off treatment, respectively. On-treatment virologic flares are described as virologic breakthrough in Section 5.3.1.1.7. On-treatment will be defined as the time period in which the participant receives any of the study interventions. Off-treatment will be defined as the period after stopping all study interventions (including NA).

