6.7. NA Re-treatment Criteria and Monitoring After Stopping of NA

After completing treatment with JNJ-3989, JNJ-6379 (or their matching placebos) and NA at Week 48 (or after premature discontinuation), participants will be monitored closely during the follow-up phase.

After stopping NA treatment, participants should be monitored as follows:

- Regular monitoring visits will be every 4 weeks during the follow-up phase in accordance with the [Schedule of Activities](#).
- A post-treatment HBV DNA value of >20,000 IU/mL should trigger re-testing of ALT/AST, HBV DNA, and total and direct bilirubin within a maximum of 7 days from receipt of the data and further repeats as necessary (ie, weekly until HBV DNA returns to <20,000 IU/mL).
- A post-treatment HBV DNA value of >2,000 IU/mL (but <20,000 IU/mL) should trigger a re-test within 14 days from receipt of the data and further repeats as necessary (ie, every other week until HBV DNA returns to <2,000 IU/mL).
- A post-treatment ALT value of >5x ULN should trigger re-testing of ALT, AST, alkaline phosphatase (ALP), total and direct bilirubin, INR, albumin, and HBV DNA on a weekly basis until ALT and AST levels have returned to <5x ULN.

After stopping NA treatment, participants should restart NA treatment:

- Immediately with signs of decreasing liver function based on laboratory findings (eg, INR, direct bilirubin) or clinical assessment (eg, ascites, hepatic encephalopathy).
- Immediately with an HBV DNA value of >100,000 IU/mL (irrespective of confirmation and/or ALT increase).
- With confirmed post-treatment HBeAg seroreversion (HBeAg positive after it was negative at NA completion).
- With confirmed* post-treatment increases in HBV DNA >2,000 IU/mL and ALT >5x ULN.
- With confirmed* post-treatment increases in HBV DNA >20,000 IU/mL.

*At least 4 weeks apart frequency of visits as described above.

Note: Additional re-testing and/or earlier restarting of NA treatment is at the investigator's discretion, even if the above cut-offs are not yet met.

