5.3.1.1.7. Virologic Breakthrough

HBV virological breakthrough is defined as having a confirmed on-treatment HBV DNA increase by >1 log₁₀ from nadir level (lowest level reached during treatment) in participants who didn't have on-treatment HBV DNA level below the lower limit of quantification (LLOQ) or a confirmed on-treatment HBV DNA level >200 IU/mL in participants who had on-treatment HBV DNA level below the LLOQ. Confirmed HBV DNA increase/level means that the criterion should be fulfilled at 2 or more consecutive time points or at the last observed on-treatment time point. On-treatment will be defined as the time period in which the participant receives any of the study interventions (including NA).

In addition, participants who experience a virologic breakthrough followed by on-treatment biochemical flare will be evaluated.

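### SAP 5.3.1.1.6 uses two unreconciled meanings of confirmed for virologic flares, so a participant restarted on NA after one HBV DNA value above 100,000 IU/mL can be placed in too low a peak category or, after a preceding value of 200 IU/mL or less, not counted

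*SAP*

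**What the plan says.** SAP 5.3.1.1.6, Derivation 1, applies to participants who are off treatment and whose last on-treatment HBV DNA was below LLOQ. It contains four rules:

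- **Start.** "The start date of a virologic flare is defined as the first date of two consecutive visits with HBV DNA > 200 IU/mL".
- **End.** The first return to 200 IU/mL or below, "or the date of treatment restart, whichever comes first".
- **Peak category.** Each flare is "categorized based on the confirmed (i.e., two consecutive values) peak HBV DNA above any of the four thresholds" (100,000, 20,000, 2,000 and 200 IU/mL) between those two dates.
- **Yes/No coding.** This uses confirmed with a footnote mark, and the footnote reads: "Confirmed means that the criterion should be fulfilled at 2 or more consecutive time points or at the last observed time point".

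Derivation 2 has the same structure, on a scale of log10 increase from end of treatment. The section adds: "The virologic and clinical flares will be assessed only off-treatment". SAP 5.3.1.3.2 dates time to flare from the earlier of two confirming visits. The neighbouring definition of virologic breakthrough (SAP 5.3.1.1.7) has a similar clause, but there the period is named: "or at the last observed on-treatment time point".

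Protocol 6.7 asks for NA restart "Immediately with an HBV DNA value of" more than 100,000 IU/mL, without waiting for a second value. Its other criterion based on HBV DNA alone, above 20,000 IU/mL, does need confirmation at least 4 weeks apart.

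**The concern.** The start and peak rules need a second off-treatment value, and the flare window closes at NA restart. At the top threshold the protocol calls for restart on the first value. For a participant managed as the protocol asks, the confirming value would often fall after the window has closed. The 100,000 IU/mL category is therefore the one that compliant restart tends to leave unconfirmed.

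Flares are a listed secondary endpoint. The same definition feeds time to flare, clinical flares (which need a virologic flare), the summaries of flares followed by NA re-treatment or by HBsAg seroclearance (SAP 5.3.2.1.3), and sequencing at the time of flare (SAP 7.1). A participant with no dated flare is censored in the time-to-flare analysis at the last available assessment, as if flare-free.

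**Working it through.** The plan states no figure for this point, so there is none to reproduce. The check applies the SAP rules to HBV DNA courses. The courses are assumed for illustration; the thresholds, retest timing and restart rule come from SAP 5.3.1.1.6 and Protocol 6.7.

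**Three readings**

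- (a) Two consecutive off-treatment values, as in the start and peak rules.
- (b) Footnote applied, with the last observed time point taken as the last in the study.
- (c) Footnote applied, with the last observed time point taken as the last off-treatment value, and extended to the start date and peak category.

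Readings (a) and (b) gave the same result in every course, because follow-up continues after restart and the last value in the study is then low.

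| Off-treatment HBV DNA, IU/mL (follow-up day) | Restart day | Readings (a), (b) | Reading (c) |
|---|---|---|---|
| A: 5 (57), 150,000 (85) | 92 | no flare | >100,000 |
| B: 1,500 (57), 150,000 (85) | 92 | flare, >200 | >100,000 |
| C: 15,000 (57), 150,000 (71) | 78 | flare, >2,000 | >100,000 |
| D: 50,000 (57), 150,000 (64) | 71 | flare, >20,000 | >100,000 |
| E: 5 (57), 150,000 (85), 300,000 (92, pre-dose) | 92 | flare, >100,000 | >100,000 |
| F: 25,000 (57), 30,000 (64), 28,000 (71), 26,000 (85) | 88 | flare, >20,000 | >20,000 |
| G: 300 (57), 300 (85) | none | flare, >200 | >200 |

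Courses A to D have one value above 100,000 IU/mL before restart. None reaches the top category under (a) or (b): three are placed lower and one is not a flare. Mild or sustained relapse (F, G) is classed the same way on every reading.

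**What a complete miss requires.** HBV DNA must rise from 200 IU/mL or less to above 100,000 IU/mL between adjacent samples:

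- Rise: log10(100,000 / 200) = log10(500) = 2.70.
- Doubling time over 28 days: 28 × ln 2 / ln 500 = 3.1 days or less.
- Doubling time over 36 days (both visits at the edge of their ±4-day windows): 36 × ln 2 / ln 500 = 4.0 days or less.

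With a slower rise, an intermediate value above 200 IU/mL starts the flare and the error is one of category.

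**Unscheduled retests.** The table counts every sample. SAP 2.1.3 keeps one measurement per visit window, the one closest to the target day, and SAP 5 ties efficacy over time to those time points. Days 85 and 92 in course E both fall in the Follow-up Week 12 window [72, 99]. Days 57 and 71 in C, and 57 and 64 in D, all fall in the Follow-up Week 8 window [44, 71]. If only windowed values count, E loses its confirming value, and C and D lose their second off-treatment value. The SAP does not say which applies to flares.

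**Does the footnote settle it?** It can turn the Yes/No code to Yes under reading (c). It does not alter the start rule, the peak rule (which spells out two values) or the dating in SAP 5.3.1.3.2. A participant could then be coded Yes with no start date and no matching category.

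**The case against.** The strongest reply is that the footnote already covers these cases. Virologic and clinical flares are assessed only off treatment, so the natural last time point is the last off-treatment one. The footnote also serves biochemical flares, assessed both on and off treatment, which may be why it names no period. This is a fair reading of the Yes/No coding. It leaves the explicit two-value rules for start date and peak unreconciled.

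Other points on that side stand and limit the size:

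- A preceding value above 200 IU/mL normally starts a flare, so most affected participants would be counted in a lower category.
- A second sample above 100,000 IU/mL drawn by the day of restart would confirm the peak, if retests count. Protocol 6.7 asks for a retest within 7 days above 20,000 IU/mL and encourages parallel local testing.
- The events are reported elsewhere. Actual restarts and each re-treatment sub-criterion are evaluated (SAP 5.3.1.1.8) and restarts are cross-tabulated against criteria met (SAP 5.3.2.1.4). HBV DNA below 100,000 IU/mL is a reported cut-off, and biochemical flares do not end at restart.
- The primary endpoint is untouched, because NA re-treatment between Weeks 48 and 72 is already non-response.

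A reader might infer that every promptly restarted participant is lost, or that flares are understated more in the arm with faster rebound. The documents support neither. They give no HBV DNA kinetics by arm and no interval from result to restart. A reader might also infer that the 100,000 flare category was created to mirror the restart rule. The SAP amendment history gives that reason for the HBV DNA cut-off in 5.3.1.1.5; for flares it says only that a threshold was added.

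**Conclusion.** The point holds as an internal inconsistency with a definite direction. Applied as written, the start-date and peak rules under-fill the category above 100,000 IU/mL when NA is restarted before a second off-treatment value above that level. Such a participant moves to a lower category, or is not a virologic or clinical flare if the preceding value was 200 IU/mL or less. The footnote repairs only the Yes/No code, and only if its last time point means the last off-treatment one.

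The number affected cannot be computed, nor can any difference between arms. The SAP amendment history ties the revised re-treatment criteria to Protocol Amendment 4 (26 November 2021), which may limit how many participants came under the single-value rule. The table rests on assumed courses and on counting all samples. The matter is worth correcting before the flare analyses are reported, but it does not bear on the primary conclusion.

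**What to change.** Use one definition of confirmed for the Yes/No coding, start date, peak category and time to flare, in both derivations. For virologic flares, and for the HBV DNA part of clinical flares, the criterion is met at two consecutive off-treatment assessments, or at a single assessment that is the last off-treatment one before NA restart or end of observation. In the single-value case that date is the flare start. State whether unscheduled retests count as consecutive assessments despite the one-value-per-window rule in SAP 2.1.3.

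The SAP has a precedent: for renal tubular markers (6.2.3.2) it accepts one abnormal measurement followed by drug discontinuation as confirmed. Keep the two-value requirement for all other peaks; grading everyone by the highest single value would go further than the problem needs.

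This changes SAP wording and programming only. It needs no new data and leaves the protocol's re-treatment criteria as they are. The cost is that a few unconfirmed single values will count as flares or as higher-category flares; a count of single-value flares by arm would make that visible.
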